## GENERAL INFORMATION

Inability to walk is one of the significant challenges that affect quality of life in individuals with chronic hemiparesis. Not only is gait an important activity of daily living, it can also help minimize many of the secondary complications seen as a result of decreased mobility resulting from neurological injury, such as cardiovascular deconditioning and loss of bone mass. Assistive devices and orthoses are utilized to assist individuals with hemiparesis to regain the ability to walk, however, efficiency of walking using these devices (assisted walking) is often overlooked. Introducing an orthotic device alters the gait kinematics. The inefficiency of assisted walking could be the result of abnormal gait kinematics and kinetic patterns which are associated with outdated product design and inadequate users' ability. With advanced technology, a novel microprocessor-controlled leg orthosis system (C-Brace, Ottobock Health Care LP) has been developed to promote assisted walking with near-to-normal gait biomechanical parameters. This device, therefore, could also improve the efficiency of assisted walking.

With the advanced technology, however, little is known about which patients would receive maximal therapeutic benefits in physiology, physical function and quality of life. Therefore, the purpose of this study is to develop a clinical algorithmic-based evaluation and treatment approach for C-Brace for use by persons with hemiparesis or hemiplegia. We are mostly interested in measuring the physiological effects, specifically neuromuscular and cardiovascular parameters, and gait characteristics during walking with C-brace. We plan to identify the strongest predictors and outcome measures of walking in persons with hemiparesis or hemiplegia using the C-brace, then develop an algorithm for reliable prognosis and early subgrouping.

## BACKGROUND INFORMATION

The impaired ability to walk independently is a significant consequence after neuromuscular injuries resulting in substantial limitation in mobility and performance of daily activities, thus restricting full participation and home and community re-integration [1]. Regaining the ability to walk is one of the priorities in rehabilitation in this population, however, walking efficiency and energy cost is often overlooked. The consequence of additional metabolic demand contributes to fatigue, which promotes a sedentary life style that predisposes an individual to secondary health deterioration and compromised quality of life.

Energy expenditure in walking is increased in persons with hemiparesis and hemiplegia [2]. Studies have indicated that energy cost in walking is affected by many factors such as ankle plantarflexors [3], quadriceps activity[4] and center of mass motion [5]. Therefore, walking with orthoses whose design is to compensate or correct an abnormality, could reduce energy expenditure [6] while different orthoses designs could also affect energy expenditures [7-9].

The knee-ankle foot orthosis (KAFO) is one of the most often prescribed to facilitate walking for patients with weakness of the muscles which control the knee and protect against loss of structural integrity of knee joint. Two most commonly utilized KAFOs are conventional KAFO and stance-control orthosis (SCO). The difference between these 2 orthoses is the knee control mechanism during walking: conventional KAFOs prevent knee flexion during stance and swing phase, while SCO prevent knee flexion during stance phase while allowing knee flexion during swing phase. The advantage of the SCO is it reduces the commonly observed gait compensatory strategies observed with use of conventional KAFO during swing phase to create sufficient toe clearance such as hip hiking, vaulting and circumduction and promotes improved gait kinematics[10-13]. As noted in the literature these gait compensations tend to increase energy expenditures [14-16]. Due to a reduction in gait deviations and compensations, walking with a SCO could lead to improved walking energy efficiency.

Although SCO allow users to have a more natural gait pattern, functional limitations remain. The most important limitation is the lack of dampened knee flexion in the weight bearing condition required to descend ramps and stairs and when transitioning from standing to sitting. Additionally the absence of knee flexion dampening in swing phase of the SCO orthosis results in an absence of stumble recovery, permitting a sudden loss of control and a fall. These limitations significantly affect the ability to perform daily activities not only at home but within the community as well. Recently a novel microprocessor-controlled leg orthosis system (C-Brace) has been developed to engage dampened knee flexion in the weight bearing condition to overcome the limitation from SCO[10]. Therefore, C-Brace could also promote assisted walking with near-to-normal gait biomechanical parameters and lead to a reduction of energy cost and improved quality of life.

To enhance the feasibility and success rate of interventional trials in gait training with C-brace, early identification of subgroups based on outcome predictors should be investigated. These outcome predictors could serve as inclusion and exclusion criteria for identifying subgroups of patients who may receive maximal therapeutic effects from using C-brace.

Therefore, the purpose of this study is to develop a clinical algorithmic-based evaluation and treatment approach for C-Brace for use by persons with hemiparesis or hemiplegia. We are mostly interested in measuring the physiological effects, specifically neuromuscular and cardiovascular parameters, and gait characteristics during walking with C-brace. We plan to identify the strongest predictors and outcome measures of walking in persons with hemiparesis or hemiplegia using the C-brace, then develop an algorithm for reliable prognosis and early subgrouping.

## OBJECTIVES

Specific Aim 1: To quantify and compare the neuromuscular, cardiopulmonary responses and gait kinematics during walking with and without C-brace in individuals with hemiparesis or hemiplegia. We plan to recruit patients with hemiparesis or hemiplegia following stroke and include a wide range of gait impairments. It is expected that subjects will demonstrate various degree of difference in energy expenditures, neuromuscular responses, functional status and gait characteristics between walking with and without C-brace, depending on their current walking ability. We hypothesize that the changes in cardiopulmonary responses, neuromuscular responses of major lower muscle groups and gait characteristics would be greater in persons with lower functional status and severe gait impairment.

Specific Aim 2: To investigate the association between gait improvement (i.e. gait kinematics, speed and walking distance) in walking with C-Brace and baseline neuromuscular, cardiopulmonary characteristics that affect gait performance, cognition and physical function in individuals with hemiparesis or hemiplegia. We also aim to develop an algorithm to characterize and subgroup the patients who receive gait training with C-Brace. We hypothesize that the improvements observed in walking with C-Brace are related to muscle strength, range of motion, severity of spasticity and the functional status, and the degree of relations may be varied. We will then identify the key parameters and measures based on association to develop an algorithm to characterize the patients who may receive the maximal benefit of using C-Brace for walking.

## STUDY DESIGN

### Subjects

15 individuals with diagnosis of stroke and residual hemiparesis or hemiplegia will be grouped into one of three categories based on their walking speed at baseline. Subjects will receive 4 weeks of gait training utilizing C-Brace, 3 times per week for a total of 12 sessions. We will utilize the 10 Meter Walk Test to assess gait speed for all groups at baseline (week 0). Once training sessions are complete and subject is considered an independent experienced user (week 5) we will assess the neuromuscular and cardiopulmonary responses and gait kinematics during walking with and without C-Brace. Subjects will then continue with use of C-Brace in their daily routine in their home and community environments for 4-6 weeks. Subjects will then return for a follow up visit (week 8-10) and reassessment of neuromuscular and cardiopulmonary responses and gait kinematics during walking with and without C-Brace.

## **Study Population**

15 individuals with hemiparesis or hemiplegia after stroke in the Houston metropolitan area. Inclusion and exclusion criteria are listed in Table 1. Participants will be screened and evaluated by study investigators and certified physical therapists. We plan to recruit individuals with a wide range of walking abilities. The walking ability will be determined by gait speed from 10 meter walk test: severe gait impairment (gait velocity <0.4 m/s, moderate gait impairment (gait speed 0.4-0.8 m/s) and mild impairment (gait speed >0.8 m/s)[17].

Table 1:

	Inclusion Criteria	Exclusion Criteria
15 subjects (5 subjects in each group) • Mild • Moderate • Severe	

• Age 18 - 65 years

• Diagnosis of hemiparesis or hemiplegia following stroke

• Presence of abnormal walking pattern

• Poor knee control during stance phase

• Cognitive ability to (or care provider) manage daily charging of battery

• Cognitive ability to follow commands

• Hip flexor muscle strength grade 3 or greater or the ability to perform reciprocal gait using compensatory patterns

• Able to operate C-brace

	

• Weight > 275 lbs. (Includes body weight and weight of heaviest object carried)

• Less than 2° of ankle motion

• Severe spasticity of the quadriceps (MAS >3) and/or uncontrolled spasticity of the quadriceps

• Severe spasticity of other lower limb muscles (MAS >3)

• Fixed genuvalgum exceeding 10° beyond anatomic neutral valgum

• Any fixed genuvarum exceeding anatomic neutral varum.

• Hip or knee flexion contractures greater than 10°

• Presence of COPD

• Chronic heart failure – NYHA stages 3 and 4

## **STUDY PROCEDURES**

### **Fitting and Training Protocols:**

Qualified participants will be fitted with the C-Brace by a certified orthotist specialist. Subjects will participate in a baseline assessment after which they will participate in training sessions for gait training from certified physical therapist(s). The length of training is 4 weeks with a total of 12 sessions (3 times per week for 4 weeks). The goal of training sessions is to progress subject's ability to walk with C-Brace over progressively more challenging environments. They will learn how to safely and independently walk with the C-Brace in the following conditions: overground walking, reciprocal slope, descending ramps and stairs and negotiation of uneven terrain. Adjustments will be made to C-Brace according to subjects ability and performance to progress them toward independence. Once subject has reached the independent/experienced user

level, they will continue to utilize the C-Brace in their home environment. Subjects will be considered as independent/experienced users when they are able to safely walk with C-Brace without a loss of balance for at least 10 meters and when they can complete this task without requiring aide from an additional assistive device or physical assistance from the therapist. Subjects will be checked off on their ability to safely ambulate in the overground environment as well as in the various conditions of slopes, ramps, steps and uneven terrain.

Once subjects are declared independent users, they will participate in a post training assessment. After training sessions have been completed, subjects will be provided with the C-Brace to use in their everyday routine for 4-6 weeks. During the home use period, subjects will continue to wear the C-Brace as they return to their normal daily activities. During this period subjects can return to see the therapist for any adjustment or re-training as needed. The daily activity will be recorded in an activity log. Subjects will return for a follow up assessment at the end of the home use training. Follow-up assessments will be scheduled at the 4 week mark, with a 2 week window allotted to allow for accommodating subject and staff schedules.

The training and assessment sessions will be conducted at UT Health Motor Recovery Laboratory at the NeuroRecovery Research Center at TIRR Memorial Hermann.

### **Specific Aim 1:**

To quantify and compare the neuromuscular, cardiopulmonary responses and gait kinematics during walking with and without C-brace in individuals with hemiparesis or hemiplegia. We plan to recruit patients with hemiparesis or hemiplegia following stroke who present with gait impairments. It is expected that subjects will demonstrate varying degrees of energy expenditures, neuromuscular responses, functional status and gait characteristics between walking with and without C-brace, depending on their current walking ability. We hypothesize that the changes in cardiopulmonary responses, neuromuscular responses of major lower muscle groups and gait characteristics will be greater in persons with lower functional status and more severe gait impairments.

### **Outcome Measures:**

We will measure the following parameters during gait with and without C-Brace at completion of training sessions and at follow up.

- *Timed Up and Go:* Assesses mobility, balance, walking ability, and fall risk in older adults. The test measures the time it takes the subject to perform a sit to stand from a chair with arms, walk to a mark on the ground 10 feet away and return to the seated position in the chair with arms. This test has been used in assessing stroke recovery with high reliability and validity[18].
- *10 Meter Walk Test (10MWT):* Measure of gait speed. Subjects will walk a total of 14 meters at their preferred walking speed and at a fast pace. The test measures the time it takes the subject to complete the middle 10 meters of the walk.
- *Kinematics and electromyography (EMG):* Bilateral upper and lower extremity kinematics and surface electromyography (sEMG) recordings will be collected during 10MWT. Infrared light emitting diode markers will be attached to bilateral lower extremities. The marker data will be recorded using the NDI Optotrak Certus motion capture system. Marker data will be processed using custom Matlab program to

determine lower extremity joint excursion and joint angular velocities. For EMG, we will place bipolar surface electrodes on the bilateral major leg muscles to record electromyography (1000Hz, Motion Labs 16-Channel EMG System). We will calculate the EMG amplitude and burst duration over the whole gait cycle during the 10MWT.

- *Six-minute walk test (6MWT):* This test assesses distance walked over 6 minutes as a sub-maximal test of aerobic capacity/endurance. It has good responsiveness to detect improvements in capacity to walk in stroke patients [19].
- *Metabolic expenditure during walking:* Oxygen consumption during 6MWT will be determined using a portable metabolic system. Metabolic data will be collected on a breath-by-breath basis during gait assessment. Prior to the testing, the system will be calibrated using room air and reference gas mixture. During the testing, the subject will wear the face mask at all times and will be asked to breathe normally. Subjects will also wear a heart rate monitor. The data will be synchronized with kinematic and electromyography data for further analysis. This task will be performed during walking with and without C-Brace.

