## DATA and SAFETY MONITORING

We will use following strategies to prevent some expected events for this study:

1) Loss of confidentiality or privacy

Information obtained for this study will be kept private to the extent allowed by law. However, research information may be shared with the University of Texas Health Science Center at Houston Institutional Review Board (IRB), the research physician investigator, the research staff and others who are responsible for ensuring compliance with laws and regulations related to research.

The study will be performed at UT Health Motor Recovery Laboratory at the TIRR NeuroRecovery Research Center. All data collection records will be locked in the Study Coordinator's office in a locked file cabinet. Energy consumption, sEMG and motion capture files will be saved to the research computer using de-identified data. All computers are password protected and therefore, only authorized persons have the access to the electronic files saved in computers and will adhere to TIRR MEMORIAL HERMANN standards.

2) Loss of saved electronic data after a computer crash

All original data will be maintained on paper data collection forms. De-identified data may be entered into computer for data analysis. A standard procedure of electronic file backup is established and enforced by the PI. All file backups are routinely performed in the local hard drive. However, if there are other unanticipated problems which occur during and after data collection: the original paper version of the data will be maintained in the locked file cabinet.

3) Muscular soreness or fatigue

*Borg Rating of Perceived Exertion Scale* (Borg) will be administrated periodically throughout the intervention sessions. Subject will be provided with rest period as needed, in particular if BORG rating  $\geq 17$ .

4) Loss of balance or fall from testing

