## STATISTICS

### Aim 1:

The effects of C-Brace on dependent variables will be analyzed using separate 2-factor (group x condition) analyses of variance (ANOVA) with repeated measures on the walking condition (walking with and without C-Brace). The model will first test for the interaction to determine if 3 groups (mild, moderate and severe) respond similarly across time. In the event of a significant interaction ( $p < .05$ ) we will test for differences between among groups at each point in time (post hoc Tukey).

[figure not shown]

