## QUALITY CONTROL and ASSURANCE

To ensure research integrity, standard written procedures for all tests will be established by the Principle Investigator and the Study Coordinator who will then assess each team member's competence for research conduction on a regular basis. Therefore, the testing protocol will be consistent throughout the entire data collection for this study.

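### The order of walking with and without the C-Brace is neither stated nor balanced, so a common order would confound fatigue or practice with the Aim 1 condition effect.

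*Combined protocol and SAP*

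**What the plan says.** Under Specific Aim 1, Outcome Measures, the protocol states: "We will measure the following parameters during gait with and without C-Brace at completion of training sessions and at follow up". The list covers the Timed Up and Go, the 10MWT with kinematics and EMG, the 6MWT, and oxygen consumption during the 6MWT. On the metabolic test it adds: "This task will be performed during walking with and without C-Brace". The Assessment Timeline places these measurements at Visit 17 (post training) and Visit 18 (follow-up), one visit for each time point.

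Statistics, Aim 1, specifies a two-factor ANOVA, group by condition, "with repeated measures on the walking condition (walking with and without C-Brace"). It has no term for order or period. Table 1 gives "15 subjects (5 subjects in each group").

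Two other sections come near the subject. Data and Safety Monitoring, under muscular soreness or fatigue, says that the Borg scale "will be administrated periodically throughout the intervention sessions" and allows rest as needed. Quality Control and Assurance says that "standard written procedures for all tests will be established by the Principle Investigator and the Study Coordinator", and that testing will therefore be consistent throughout data collection. Neither mentions the order of the two walking conditions. No section does.

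**The concern.** The study has no parallel control group, so the difference between the two conditions in the same subject is the only Aim 1 estimate of what the device does. Both conditions are measured at the same visit, so one must come second. Fatigue would penalise the second condition and practice would favour it, so the direction of any bias is unknown. If the order is the same for everyone, the expected paired difference is the device effect plus the order effect. No analysis of those data can separate the two, and a larger sample would not reduce the bias.

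Fatigue is not a remote possibility by the protocol's own account. The Background links the extra metabolic demand of walking to fatigue, and the safety section lists fatigue as an expected event. The Aim 1 hypothesis is that changes are greater in more impaired subjects, and an order effect that varied with severity could imitate or hide that pattern.

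**Working it through.** The plan gives no power, effect size or SD, so there is no figure of its own to reproduce. The calculation shows what a fixed order could do.

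**Inputs**
- n = 15, 5 in each of 3 groups (Table 1). Error df for the paired differences: 15 − 3 = 12.
- Alpha 0.05. Statistics, Aim 1, states it for the interaction; I assume a two-sided 0.05 for the condition main effect.
- True device effect zero.
- Order effect d, in SDs of the paired difference D (with minus without C-Brace). This is an assumption, shown over a range.

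**Condition main effect, one fixed order.** E[D] = device effect + d. The test statistic is noncentral t with 12 df and noncentrality d × √15; the critical value is 2.179.

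| d | d × √15 | False-positive rate |
|---|---|---|
| 0 | 0 | 5% |
| 0.2 | 0.775 | 11.0% |
| 0.4 | 1.549 | 29.7% |
| 0.5 | 1.936 | 42.9% |
| 1.0 | 3.873 | 94.4% |

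**Group-by-condition interaction, one fixed order.** Noncentral F with 2 and 12 df and noncentrality λ = 5 × Σ(d_g − mean d)², where d_g is the order effect in group g. A uniform order effect gives λ = 0, so the rate stays at 5%.

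| d in mild / moderate / severe | λ | False-positive rate |
|---|---|---|
| 0.1 / 0.2 / 0.3 | 0.100 | 5.6% |
| 0.2 / 0.4 / 0.6 | 0.400 | 7.4% |
| 0 / 0.25 / 0.5 | 0.625 | 8.9% |
| 0 / 0 / 0.5 | 0.833 | 10.3% |
| 0 / 0.5 / 1.0 | 2.500 | 22.1% |
| 0 / 0 / 1.0 | 3.333 | 28.3% |

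**What balancing leaves at one visit.** The residual is the difference between the two order counts divided by n.
- 3:2, 2:3, 3:2 across groups is 8:7 overall: (8 − 7)/15 = 1/15 of the order effect.
- 3:2 in the same direction in all three groups is 9:6: (9 − 6)/15 = 1/5.
- Within any group of five: (3 − 2)/5 = 1/5, in either direction.

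**What the order term adds.** With the 8:7 split and d from 0 to 1.0 (20,000 simulated studies for each value):
- Without an order term, the order effect stays in the error. The false-positive rate for the main effect falls from 4.5% at d = 0.25 to 0.5% at d = 1.0, so the test becomes conservative.
- With an order term, the bias is about zero and the rate is 4.6% to 5.2%. Error df fall from 12 to 11.

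A single order term removes the order effect that the groups share. If the effect differs by group, each group of five keeps about 1/5 of its departure from the fitted common effect at a visit. Reversing the order at Visit 18 addresses that part.

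**The case against.** The strongest reply is that silence is not a fixed order. The written test procedures promised under Quality Control and Assurance could set or balance the order. That is fair: a reader might infer that one order will be used for everyone, and the documents do not say so. They do not say the opposite either, and testing that is consistent throughout could equally mean a single order. The gap stands and the bias is conditional.

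Second, a reader might carry the 11% to 43% over to the interaction, which the plan tests first. That is not supported. Those rates belong to the condition main effect. The interaction stays at 5% under a uniform order effect, and nothing in the documents shows that the order effect is larger in the severe group.

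Third, the outcomes are not equally exposed. The Timed Up and Go and the 10MWT are short, and EMG and kinematics are recorded during the 10MWT. By Visit 17 subjects have done the walking tests at baseline and have had 12 training sessions, which reduces practice effects. This narrows the point mainly to the 6MWT and oxygen consumption, although a preceding 6MWT could carry over into the short tests.

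Fourth, Borg ratings and rest as needed offer some protection. The Borg sentence is written for the intervention sessions, and rest as needed may differ between the two conditions, so this mitigates only in part.

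Last, this is a 15-subject study, and its Clinical Algorithm section says a larger one is needed to set the criteria. That limits the weight of the point, but not the case for a cheap correction.

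**Conclusion.** The point holds as a design risk, not as a demonstrated bias. The order of conditions is unstated and unbalanced, and the Aim 1 model has no order term. If one order is used for all, the order effect is fully confounded with the condition effect and cannot be recovered at analysis.

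The size depends entirely on an order effect that the documents do not give. At 0.2 to 0.5 SD of the paired difference, the condition main effect is falsely significant in about 11% to 43% of studies instead of 5%. The interaction is much less sensitive: about 6% to 10% when the order effect differs between groups by up to 0.5 SD, and 22% to 28% only with 1.0 SD in the severe group. These rates assume no device effect, 15 complete subjects and normally distributed differences with equal variance. The change should be made before Visit 17 testing starts.

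**What to change.** In Specific Aim 1, Outcome Measures:
- Randomise which condition is tested first, within severity group, with splits of 3:2, 2:3 and 3:2 so that the total is 8:7.
- Reverse each subject's order at Visit 18.
- Use the same minimum rest between conditions for all subjects.
- Record the order used.

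In Statistics, Aim 1:
- Add test order as a fixed effect. It is needed because each group of five keeps 1/5 of the order effect at a visit.
- State how Visits 17 and 18 are combined. The reversal cancels the order effect only if that effect is similar at both visits, subjects complete both, and the analysis combines them. The current two-factor model does not say that it does.

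The cost is one error df in the single-visit model (12 to 11), a 15-line order list, and sessions in which the brace is taken off midway instead of put on. No extra visits or subjects are needed.

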### **Specific Aim 2:**

To investigate the association between the gait improvement (i.e. gait speed and walking distance) in walking with C-Brace and baseline neuromuscular, cardiopulmonary characteristics that affects gait performance, cognition and physical function in individuals with hemiparesis or hemiplegia. We also aim to develop an algorithm to characterize the patients who may receive the maximal benefit of using C-Brace for walking. We hypothesize that the improvements observed in walking with C-Brace are related to muscle strength, range of motion, severity of spasticity and the functional status and the degree of relations may be varied. We will then identify the key parameters based on association to develop an algorithm to characterize the patients who may receive the maximal benefit of using C-Brace for walking.

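### Oxygen consumption in a six-minute walk with no stated pace does not measure the walking efficiency that motivates the study; gross oxygen cost per metre should be added

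*Combined protocol and SAP*

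**What the plan says.** The protocol and SAP are one combined document.

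- **Oxygen measure.** In the Outcome Measures under Specific Aim 1, the metabolic item states: "Oxygen consumption during 6MWT will be determined using a portable metabolic system". A heart rate monitor is also worn. No unit, averaging window or cost per metre is given.
- **Pace.** The same list says of the 6MWT: "This test assesses distance walked over 6 minutes as a sub-maximal test of aerobic capacity/endurance". Walking pace is specified for the 10 Meter Walk Test but not for the 6MWT.
- **Analysis.** Statistics, Aim 1, uses a separate two-factor ANOVA (severity group by condition) for each dependent variable, with "repeated measures on the walking condition (walking with and without C-Brace". There is no speed or distance term.
- **Hypothesis.** Specific Aim 1 expects that "changes in cardiopulmonary responses, neuromuscular responses of major lower muscle groups and gait characteristics will be greater in persons with lower functional status". It also expects energy expenditure and gait characteristics to differ between walking with and without the brace.
- **Rationale.** General Information says: "This device, therefore, could also improve the efficiency of assisted walking". Background Information argues that "walking efficiency and energy cost is often overlooked" and that the device may "lead to a reduction of energy cost and improved quality of life".

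**The concern.** The rate at which a walker uses oxygen depends on how much each metre costs and on how many metres are covered per minute. The rationale concerns the first; the planned variable mixes the two. The 6MWT is scored by distance, so pace is presumably free, and the plan expects gait to differ between conditions.

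Two consequences follow. A subject who walks faster and more economically with the brace may show unchanged or higher consumption. And if the change in speed differs between the mild, moderate and severe groups, the group by condition interaction in consumption may reflect speed rather than energy cost, or may miss a real difference in cost. That interaction is the test of the Aim 1 hypothesis.

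**Working it through.** **Inputs.** The documents give no oxygen values, no with-versus-without speeds and no SDs, so there is no stated figure to reproduce. All of the following are assumptions:

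- walking uptake without the brace, U0 = 10 mL/kg/min (8 and 7 are also used in step 5);
- resting uptake, R = 2.5, 3.5 or 4.5 mL/kg/min;
- speed gain with the brace, x = 5% (mild), 10% (moderate), 20% (severe).

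**Model.** Uptake = R + net cost per metre × speed. Gross cost per metre = uptake ÷ speed. Whether consumption is reported as a rate or as a six-minute total makes no difference, because the duration is fixed.

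**1. Threshold.** If cost per metre falls by a fraction q and speed rises by x, consumption falls only if (1+x)(1−q) < 1, that is, q > x/(1+x). This holds for gross and for net cost, at any R.

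- 0.05/1.05 = 4.8%
- 0.10/1.10 = 9.1%
- 0.20/1.20 = 16.7%

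**2. An interaction can be hidden.** Suppose cost falls by exactly 4.8%, 9.1% and 16.7% in the three groups. Consumption then changes by zero in every group, while cost per metre shows the whole gradient. This is the boundary case, chosen to show that it can happen.

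**3. An interaction can be created.** Suppose net cost falls by the same 10% in every group. Consumption changes by (10−R) × [(1+x) × 0.9 − 1] = (10−R) × (−0.055, −0.010, +0.080).

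- At R = 3.5: −0.36, −0.07 and +0.52 mL/kg/min.
- Spread between groups = 0.135 × (10−R): 1.01, 0.88 and 0.74 for R = 2.5, 3.5 and 4.5.

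**4. Gross cost also depends on speed, but less.** Suppose net cost does not change at all.

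| Quantity | Formula | R | +5% | +10% | +20% |
|---|---|---|---|---|---|
| Gross cost per metre | −(R/10) × x/(1+x) | 2.5 | −1.2% | −2.3% | −4.2% |
| | | 3.5 | −1.7% | −3.2% | −5.8% |
| | | 4.5 | −2.1% | −4.1% | −7.5% |
| Consumption | (1−R/10) × x | 3.5 | +3.3% | +6.5% | +13.0% |

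At a 20% gain the change in consumption is +15.0% for R = 2.5 and +11.0% for R = 4.5, so it exceeds the change in gross cost across this range of R.

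**5. Subtracting an assumed resting uptake.** If 3.5 is subtracted and the true value is R, the remaining artefact is (3.5−R) × x / [(1+x)(U0−3.5)]. For x = 0.20 and R = 2.5 or 4.5:

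- U0 = 10: ±0.20/(1.20 × 6.5) = ±2.6%
- U0 = 8: ±0.20/(1.20 × 4.5) = ±3.7%
- U0 = 7: ±0.20/(1.20 × 3.5) = ±4.8%

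**6. Scale.** For U0 = 10, a 10% reduction in gross cost is 0.1 × 10/(60 × 0.3) = 0.056 mL/kg/m at 0.3 m/s but 0.1 × 10/(60 × 1.0) = 0.017 at 1.0 m/s. The groups are defined by speed, so on the raw scale an equal proportional change would look like an interaction. The log scale avoids this.

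**The case against.** The strongest reply is that consumption already does what Aim 1 asks. The aim is worded as cardiopulmonary response and energy expenditure; efficiency appears in the rationale, not as an objective. Distance is collected in both conditions, so a cost per metre could be computed later and no data are lost. This stands, and it limits the point. A reader might infer that the Aim 1 oxygen measure is invalid, or that the plan will report consumption as efficiency; the documents say neither. What remains is that two separate ANOVAs, one on consumption and one on distance, give neither the within-subject ratio nor its interaction test, and a metric chosen after the data are seen carries less weight.

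A second reply is that a speed gain with the brace is not established. Aim 2 speaks of "the gait improvement (i.e. gait speed and walking distance) in walking with C-Brace", but its outcome list has the walking tests done at baseline and follow-up without the brace, so it does not establish a same-visit difference between conditions. That also stands. The support is only that Aim 1 expects gait to differ between conditions; the sizes of the gains are assumed. If speed were lower with the brace, the distortion would run the other way.

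A third reply is that pace, unit and window may be in the written test procedures promised under Quality Control and Assurance. They may be, but those procedures govern conduct and would not add a dependent variable to the analysis.

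Finally, gross cost is itself affected by speed. Step 4 confirms this, so it must be reported with speed and with the resting-uptake check.

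**Conclusion.** The point holds as a gap between rationale and measurement. The plan has a valid cardiopulmonary response but no planned variable for walking efficiency or energy cost, and its metabolic contrast and interaction are confounded with any speed difference between conditions. The threshold x/(1+x) depends only on the size of the speed change. The other figures depend on the assumed uptakes and gains and show direction and possible size. They do not show how often an interaction would be created or hidden in groups of five.

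A reader might also infer that the distortion favours, or works against, the Aim 1 hypothesis. The documents do not support that: the hypothesis says changes will be greater in more impaired subjects and gives no direction. The harm is confined to reading the metabolic result as efficiency. The Aim 2 regression is untouched, since oxygen consumption is not among its listed predictors. The change should be made, but the point does not invalidate Aim 1.

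**What to change.** In the Aim 1 Outcome Measures and in Statistics, Aim 1:

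- Add gross oxygen cost per metre: oxygen uptake divided by speed over the same stated window of the same 6MWT, with the same body-mass convention in both conditions. Analyse it on the log scale by the same group by condition ANOVA.
- Keep consumption as the cardiopulmonary response, state its unit and window, and report cost, consumption and 6MWT speed side by side.
- State that gross cost falls as speed rises even when net cost is unchanged, so a group difference in gross cost must be read with the speed changes.
- As a sensitivity check, recompute cost after subtracting an assumed resting uptake of 2.5, 3.5 and 4.5 mL/kg/min, and note that the residual artefact grows as walking uptake falls. True net cost would need a resting measurement, which the plan does not describe.

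Cost: no new measurement if the window is the whole six minutes, since uptake and distance come from the same test; a shorter window needs the distance covered within it to be recorded. The analysis grows by one ANOVA, three sensitivity recalculations and a few sentences.
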